5.3.2 Pre-Treatment Adverse Events

A pre-treatment AE is the AE with an onset time that is prior to the treatment period, but after the informed consent is obtained.

5.3.3 Treatment-Emergent Adverse Events

The treatment-emergent AE (TEAE) is defined as one of the following;

- An AE that occurred during the treatment period or the follow-up period. In the process of collecting the onset dates of AEs, an AE that occurs after the initiation of trial medication on Day 1 (the first day of the treatment period) should be treated as a TEAE. All AEs occurring on the day of first dose will be considered as TEAE if the time of AE occurrence relative to the dosing is unknown.
- An AE present prior to the treatment period that worsened in severity during the treatment period or the follow-up period.
- Any events that are present prior to the treatment period and have recovered, but recurred during the treatment period or the follow-up period should be considered as new TEAEs.

5.3.4 Medical History

A complete medical history will be obtained at the Screening Visit (Visit 1) and will include evaluations for past or present conditions. Specifically, any known history of psoriatic arthritis and scalp psoriasis will be documented at Visit 2.

Any pre-existing conditions detected at Visit 1 (e.g., abnormalities in ECG, physical examination, vital signs and laboratory tests) are considered medical history.

5.3.5 Study Medication Compliance

Total number of tablets taken will be recorded in the eCRF for the corresponding intervals as scheduled in [Table 1](#). Compliance of the study medication will be calculated as follows:

$$\text{Compliance (\%)} = \frac{\text{Total tablets taken}}{\text{Treatment duration} \times 4} \times 100\%$$

Compliance will be calculated for the treatment duration by visits, and the entire treatment period.

5.3.6 Clinical Laboratory Results

Hematology, coagulation, serum biochemistry and urinalysis are collected as scheduled in Table 1. The following information will be derived for each of the hematology, coagulation, serum biochemistry, urinalysis and other parameters:

- Change from baseline at all post-baseline visits
- Classification relative to the normal range ('Low', 'Normal' or 'High')
- Treatment-Emergent potentially clinically significant (PCS) abnormalities, if applicable

In addition, viral serology, drugs of abuse and alcohol screen, glycosylated hemoglobin (HbA1c), pregnancy test, Follicle-stimulating Hormone (FSH), QuantiFERON®-TB Gold-In-Tube test and chest radiography will also be obtained at the corresponding scheduled visit, respectively.

5.3.7 Vital Signs

Vital signs and body weight are collected as scheduled in Table 1. Vital signs include systolic/diastolic blood pressure, heart rate, respiratory rate and body temperature (°C). Subjects must rest in a sitting position for at least 5 minutes in preparation for blood pressure and heart rate assessments. The following information will be derived for all vital signs and body weight:

- Change from baseline at all post-baseline visits
- Treatment-emergent PCS abnormalities, if applicable

5.3.8 12-Lead ECG

Twelve-lead ECG recordings and conduction intervals including RR, PR, QRS, QT and Fridericia-corrected QT interval (QTcF) are obtained according to the schedules summarized in **Table 1**. The QTcF (Fridericia's formula, QTcF = QT/RR^{1/3}) will be derived and reported in the database.

The following information will be calculated for each of the 12-lead ECG measurements:

- Change from baseline to all post-baseline visits
- Treatment-emergent PCS abnormalities, if applicable

The overall clinical interpretation of an ECG is assessed as follows: normal, abnormal not clinically significant or abnormal clinically significant.

5.3.9 Physical Examination

[figure not shown]
The physical examinations will be performed by a physician or a qualified designee according to the schedule summarized in Table 1 and will include examination of the following body systems: general appearance, skin (including hair and nails), HEENT (head, ears, eyes, nose, throat), neck/thyroid, chest/lungs, cardiovascular, gastrointestinal, neurological, psychiatric/emotional, lymphatic and musculoskeletal systems.

Clinically significant abnormal physical examination findings will be recorded as medical history or AE where appropriate.

5.4 Pharmacokinetic (PK) Parameters

The pharmacokinetic parameters are:

- Trough plasma levels of JTE-451;

5.6 Medications/Procedures

At each study visit, investigators will review concomitant medications and procedures with the patients. The World Health Organization (WHO) Drug Dictionary version Global B3 March 2020 or later will be used to classify medications by preferred term, chemical ingredient names and WHO Level 3 Anatomical Therapeutic Chemical (ATC) classification of trade name. Medication

records will be characterized as prior medication and/or concomitant medication based on the subjects' start and end date of the study drug.

5.6.1 Prior Medications/Procedures

Prior medications/procedures are defined as any medications/procedures started and ended before the first dose of the study drug.

5.6.2 Concomitant Medications/Procedures

Any medications/procedures that begin before the start of the first dose of study drug and continue past that, or that begins on or after the first dose of study drug and up to 28 days after last dose of the study drug will be considered as concomitant medications/procedures.

6. STATISTICAL METHODOLOGY

Titles and headers of all statistical analysis tables will indicate the corresponding study population; the number of subjects for the population and for each treatment will be presented in the tables. Summary statistics for continuous parameters will include the number of subjects with non-missing data (n), mean, standard deviation (SD), median, minimum and maximum. For plasma concentrations, summary statistics will also include the coefficient of variation (CV%). Summary statistics for discrete parameters will include frequency count and percentage of which the denominator will be clearly indicated in the analysis table.

For efficacy and safety summaries, mean and median will be presented to 1 more decimal than the source data; SD will be presented to 2 more decimals than the source data; minimum and maximum will be presented in the same precision as the source data. Percentages including response rate will be presented to 1 decimal, e.g., xx.x%. P-values will be presented to 3 decimals. P-values greater than 0.999 will be presented as >0.999; p-values less than 0.001 will be presented as <0.001.

For figures, the corresponding study population will be displayed in the titles. All collected observations will be included in the related listings.

Baseline value is defined as the last non-missing value prior to the first dose. If the scheduled Day 1 value (i.e., not unscheduled or repeat measurement on Day 1) is available, the scheduled Day 1 value will be the baseline, as all procedures are to be performed before dosing at each visit.

[figure not shown]
The determination of baselines and EOT values for both efficacy and safety variables will be based on available scheduled assessments and unscheduled assessments. Only assessments from scheduled visits will be used for the by-visit summary tables, however, data collected from both scheduled and unscheduled visits will appear in the subject listings.

When calculating percent change from baseline in efficacy analyses, if the baseline value is 0 and the post-baseline value is also 0, then the percent change from baseline is set to 0. If the baseline value is 0 or missing and the post-baseline value is non-zero or missing, then the percent change from baseline is set to missing.

6.1 Sample Size

Approximately 150 eligible subjects (50 subjects in each treatment group) will be randomized into the double-blind treatment period.

The sample size estimation is based on the primary efficacy parameter of the proportion of subjects achieving PASI-75 at EOT.

Taking into consideration a 15-20% treatment discontinuation rate, about 50 subjects per group will be randomized into the double-blind treatment period.

6.2 Subject Disposition Summary

Subject disposition will be summarized and tabulated by treatment group and in total. The number and percentage of subjects in the safety, ITT, PP and PK populations will be tabulated. Discontinued patients and the reasons for discontinuation will be summarized. The number of subjects at each scheduled visit will be tabulated for the ITT population by treatment group and in total.

6.3 Demographics and Baseline Characteristics

Demographics and baseline characteristics as defined in Section 5.1 will be presented by treatment group with descriptive statistics for the safety, ITT and PP populations.

6.4 Efficacy Analysis

Analyses of primary and secondary efficacy parameters will be performed for both the ITT and PP populations, respectively.

For efficacy analyses, the JTE-451 treatment period is defined as the time period from the first dose of study drug to the last dose of study drug plus 4 days. The EOT value is defined as the last value taken during the JTE-451 treatment period. For PASI-50/75/90 and sPGA response analyses at EOT, if 10% or more subjects take any other psoriasis treatment that is listed in the protocol Section 3.5.5.1.1, a sensitivity analysis will be conducted using an alternative EOT value. The data used for the alternative EOT value determination will be up to and excluding the start of the other psoriasis treatment. The alternative EOT value will be the last value within 4 days after the last dose of JTE-451 in this data cutoff.

All analyses will be performed two-sided at the 5% significance level. No formal multiple comparison adjustment will be made for secondary efficacy parameters. The estimated treatment

effect (relative to placebo) from the model, along with a two-sided 95% confidence interval (CI) and p-value, will be tabulated where appropriate.

Graphical presentations of the treatment profile will be provided for the primary and secondary efficacy parameters. Sensitivity analysis and model fit assessment may be conducted, and data transformation may be employed if appropriate.

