6. Protocol Violation: the subject is non-compliant with regard to this protocol (other than the withdrawal criteria 4 and 5 listed above), as determined by Sponsor, Medical Monitor or the Investigator on a case-by-case basis.
7. Lost to Follow-up: the subject does not come for a scheduled visit and site staff makes at least 3 attempts, including a formal letter, to contact the subject over 4 weeks from a scheduled visit with no success.
8. Study Terminated by Sponsor: the Sponsor may suspend or terminate the study or part of the study at any time for any reason.
9. Pregnancy
10. Investigator Decision: the Investigator decides a subject should be discontinued for any reasons other than listed above (actual reason must be documented by site).
11. Other: actual reason must be documented by site.

Subjects who are removed from the study or withdraw consent to participate in the study after receiving at least one dose of study drug will be requested to complete an Early Termination Visit at which time the subject will undergo all the procedures described for Visit 7. Every effort should be made to perform the Visit 7 procedures as soon as possible after the last dose of study drug and the decision of discontinuation is made and prior to any changes made in the subject's anti-psoriasis therapy. Additionally, at approximately 4 weeks after study drug discontinuation, subject should return for a Follow-up Visit, where all procedures described for Visit 8 should be performed.

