3.5 Study Procedures

[figure not shown]

Figure 1. Study Schema

Table 1. Schedule of Study Procedures

	Screening Period	Treatment Period							Follow-up Period
Duration/ Study Week (Day) ^a	Up to 4 weeks	Week 0 (Day 1)	Week 2 (Day 14±2)	Week 4 (Day 28±2)	Week 8 (Day 56±4)	Week 12 (Day 84±4)	Week 16 (Day 112±4)	Week 20 (Day 140±4)	
Visit	1	2	3	4	5	6	7	8	
Informed Consent ^b	X								
Inclusion/ Exclusion Criteria	X	X							
Medical History	X	X							
Demographic Information	X								
Review Prior/ Concomitant Medications	X	X	X	X	X	X	X	X	
Physical Exam	X	X	X	X	X	X	X	X	
Vital Signs including Weight	X	X	X	X	X	X	X	X	
Height and Calculate BMI	X								
12-Lead ECG	X	X		X				X	
Chest Radiography ^c	X								
Quantiferon-TB Gold Plus Test	X								
Drugs of Abuse Screen	X								
Viral Serology	X								
FSH ^d	X								
Pregnancy Test ^d	X	X	X	X	X	X	X	X	
HbA1c	X								
Serum Biochemistry	X	X	X	X	X	X	X	X	
Hematology	X	X	X	X	X	X	X	X	
Urinalysis	X	X	X	X	X	X	X	X	
Coagulation	X	X	X	X	X	X	X	X	
Psoriasis Body Surface Area	X	X	X	X	X	X	X	X	
PASI	X	X	X	X	X	X	X	X	
sPGA	X	X	X	X	X	X	X	X	
Skindex 16	X	X	X	X	X	X	X	X	
Itch NRS ^e									
Digital Photography ^f		X					X		
Randomization using IWRS		X							
Access IWRS and Dispense Study Drug ^g		X	X	X	X	X			
Collect Study Drug and Check Compliance ^j			X	X	X	X	X		
Study Drug Administration ^k		X	X	X	X	X			
JTE-451 PK Blood Samples ^l		X		X	X	X	X		
Document Adverse Events ^m	X	X	X	X	X	X	X	X	

Note: All study procedures should be performed at each study visit prior to study drug administration; except for appropriate PK sample collection procedures as discussed below (see [Figure 2](#)). When scheduled at the same time points, ECG and vital sign parameters collection activities should be performed prior to (or at least 15 minutes after) procedures involving venipuncture [REDACTED]

- a. The target day for each visit after randomization will be calculated relative to the date of Visit 2. Every attempt should be made to have the subject attend each visit within the windows specified in the table. The study site is encouraged to make a reminder phone call to the subject before the scheduled visit. However, if a subject is unable to attend a visit within the specified windows, the visit should be scheduled as closely as possible to these windows. A subject should not skip a protocol-specified visit due to scheduling difficulties.

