Subjects will be administered the first dose of study drug at the site, upon completion of all pre-dosing procedures and randomization at Visit 2; subsequently, they will be instructed to self-administer study drug BID, at approximately 12-hour intervals, regardless of meals. However, subjects should not take study drug on the day of a study visit until after all study procedures have been completed (except for post-dose PK samples collection as shown in [Figure 2](#)). On study visit days, subjects should take their scheduled study treatment at the site, under the supervision of the investigator or designee after all required procedures prior to administration have been performed (except for Visit 7, when no study drug will be administered, as the last dose will be taken the day prior to the visit). If the subject inadvertently took study drug on the day of the study visit, prior to all required procedures, he/she may complete the visit and the actual date and time of the last dose prior to the PK blood samples collection will be accurately recorded.

Exact date and time of the last two doses prior to the pre-dose/trough PK sample collection at Visits 4 through 7 and the dosing time at the site should be documented at each visit during the Treatment Period (i.e., Visits 2 through 6).

Study drug will not be administered and all remaining study drug will be collected from the subjects at Visit 7.

If a subject discontinues the study prematurely after receiving at least one dose of study drug, an Early Termination Visit should be completed at which all procedures listed for the Visit 7 should be performed, if possible, prior to any changes made in the subject's anti-psoriasis therapy.

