4.3 Per Protocol (PP) Population

The PP population is a subset of the ITT population in which subjects do not have any major protocol deviations as listed below:

1. Dosing compliance not in 80%-120% (based on actual dosing period)
2. Subject's last dose not between Days 90-134
3. Subject did not take 360-536 tablets in total
4. >4 days between last dose and last non-follow-up efficacy assessment
5. Not meeting Inclusion Criterion #2, #3 or #4
6. Meeting Exclusion Criterion #1, #2, #3, #4, #5 (details shown below) or #10
7. Subject took “key” prohibited concomitant medications or had unstable background therapy that could potentially affect efficacy results/interpretation
 - Use of restricted medications listed in Table 2 of the protocol in the prohibited period
 - Use of prohibited medications listed in Table 4 and Table 5 of the protocol in the prohibited period. The exclusion decision will be made based on the review of the individual case and will be documented
8. Subject took incorrect study medication, e.g. due to incorrect drug dispense
9. Significant procedural deviations/non-compliance that could potentially affect efficacy results/interpretation

A pre-analysis meeting will take place after all data have been entered into the database and cleaned, but before the release of the randomization code, to identify the PP population. The decisions made to select the PP population will be documented.

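### For early discontinuers, an Early Termination PASI taken more than 4 days after the last dose is dropped from the primary endpoint and replaced by an older one, and the protocol gives sites no matching time limit

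*SAP*

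**What the plan says.** **Timing of the visit.** For subjects removed early, Protocol 3.4 asks sites to make every effort to "perform the Visit 7 procedures as soon as possible after the last dose of study drug and the decision of discontinuation is made", and before any change in anti-psoriasis therapy. Protocol 3.5.3 adds that "an Early Termination Visit should be completed at which all procedures listed for the Visit 7 should be performed, if possible". Neither section gives a number of days, and Protocol Table 1 has no Early Termination column or window.

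**The EOT value.** SAP 6.4 defines the treatment period for efficacy as "the time period from the first dose of study drug to the last dose of study drug plus 4 days" and continues: "The EOT value is defined as the last value taken during the JTE-451 treatment period". SAP 6 says which assessments are eligible: "The determination of baselines and EOT values for both efficacy and safety variables will be based on available scheduled assessments and unscheduled assessments". The primary parameter is PASI-75 at EOT.

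**Missing data.** SAP 6.4.7 scores a subject as a non-responder at EOT only when the EOT value is missing.

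**Per-protocol set.** SAP 4.3 lists as a major deviation ">4 days between last dose and last non-follow-up efficacy assessment". The same 4 days therefore appear there, but only as a reason to leave the PP population.

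**The concern.** The Early Termination visit repeats the Visit 7 procedures, so it records PASI when the subject stops. The protocol ties it to the last dose and also to the decision to discontinue. A subject may stop tablets at home and tell the site a week later. The site can then act at once and still miss a 4-day limit that the readable protocol never mentions.

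The trial then holds a PASI close to stopping but classifies the subject on an older one. Stopping may be related to outcome: the note under Table 2 in Protocol 3.5.5.1.1 allows study drug to be withdrawn for a significant clinical exacerbation of psoriasis. Such a subject could still show PASI-75 at the earlier visit. Equally, a subject who first reached PASI-75 after that visit would be scored a non-responder.

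**Working it through.** **Inputs.** Nominal visit days are 14, 28, 56, 84 and 112, with windows of ±2 days at Weeks 2 and 4 and ±4 days at Weeks 8, 12 and 16 (Protocol Table 1). The EOT cut-off is last dose + 4 days (SAP 6.4). About 50 subjects per arm are planned, with 15-20% discontinuing treatment (SAP 6.1).

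**1. The plan's own figure.** The sample size cannot be reproduced, because the readable text gives no PASI-75 rates or power. The dropout allowance is coherent: 40/(1 − 0.20) = 50 and 42/(1 − 0.15) = 49.4, rounded up to 50. So 50 per arm fits about 40-42 completers.

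**2. One subject.** The last dose is on Day 80 and the Early Termination visit on Day 86. The cut-off is 80 + 4 = Day 84, so the Day 86 PASI is not eligible. With Week 8 held on Day 56, EOT is the Day 56 value: 80 − 56 = 24 days before the last dose and 86 − 56 = 30 days before the unused PASI.

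**3. Age of the retained value.** Age = last-dose day − day of the last eligible PASI, with no unscheduled PASI in between.
- Nominal days, next scheduled visit not held: 83 − 56 = 27 days at most. The intervals 28-56 and 84-112 give the same maximum.
- Within windows: Week 8 on Day 52, last dose on Day 87 (the day before the latest Visit 6 day), giving 87 − 52 = 35 days. The cut-off is Day 91. A PASI on Day 92 is unused and lies 92 − 52 = 40 days after the retained one.
- If a scheduled visit within 4 days after the last dose is still held, the nominal maximum falls to 79 − 56 = 23 days.
- If last-dose days are spread evenly over Days 14-111 (assumption) and the next visit is not held, the mean age is 12.5 days, and 42 of 98 days (43%) give 14 days or more.
- If the last dose falls on Days 1-13 (Days 1-9 if the Week 2 visit is still held within 4 days), no post-baseline value is eligible. The subject is a non-responder and the problem does not arise.

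**4. Whether another rule covers these subjects.**
- Non-responder imputation does not, because EOT is present.
- The alternative-EOT analysis in SAP 6.4 does not. It runs only if 10% or more of subjects take other psoriasis treatment, and it keeps the same 4-day limit.
- The PP analysis removes them but does not isolate the effect. SAP 4.3 criterion 2 already excludes anyone whose last dose falls before Day 90, so both examples above leave the PP set regardless of the gap.
- SAP 6.4.7 allows further sensitivity analyses of PASI-75 at EOT but does not require or specify any.

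**5. Size.** Planned discontinuations per arm are 50 × 0.15 = 7.5 to 50 × 0.20 = 10. One subject is 1/50 = 2 percentage points.

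The sensitivity to two changed classifications in the active arm is shown below. The rates are assumptions. Power is for 50 per arm, two-sided 5%, without stratification.

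| Placebo vs active | Power | Two responders lost | Two responders gained |
|---|---|---|---|
| 5% vs 25% | 81% | 67% | 90% |
| 10% vs 35% | 86% | 75% | 93% |
| 10% vs 40% | 95% | 88% | 98% |

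**The case against.** **The 4-day limit is a defensible on-treatment definition.** It matches the ±4-day window at Weeks 8-16, and Protocol 1.3.2 says the drug clears within about one day. A later PASI is off drug. This stands, and it is a reason to keep the primary definition. It does not remove the need to show what the rule does to the result.

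**The affected subjects are identifiable.** PP criterion 4 picks them out, and SAP 6.4 runs the primary analysis on both ITT and PP. This stands too, so it would be wrong to say the plan is blind to them. However, the ITT primary analysis neither counts nor tests them.

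**Not every discontinuer is at risk.** A subject lost to follow-up is unlikely to have an Early Termination PASI to drop. Some stops are decided at a scheduled visit where PASI is taken that day. Stops before Week 2 generally become non-responders. This stands: 7.5-10 per arm is a ceiling. A reader might assume that a quarter to a half of these visits are late and infer about 2-5 subjects per arm (7.5 × 0.25 = 1.9 to 10 × 0.5 = 5). The documents give no late-visit rate, so that range has no support.

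**Completers.** A reader might infer that completers lose their Week 16 PASI as well. Dosing is described as lasting 16 weeks, and for a visit that cannot be held in its window Table 1 footnote a says "the visit should be scheduled as closely as possible to these windows". A subject who stopped on Day 112 and attended on Day 117 would be outside the limit. The documents do not support this for a subject who follows the protocol. Table 1 footnote k states the 16 weeks and, in the same item, puts the last dose on the day before Visit 7. Protocol 3.5.3 repeats this. The SAP reads it the same way: PP criteria 2 and 3 accept a last dose up to Day 134 and up to 536 tablets, which is 134 × 4. The gap is then one day, and the dosing passages do not conflict.

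**Direction.** A reader might infer that the rule inflates response rates. It can equally miss late responses, so no direction can be claimed.

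**Conclusion.** The point holds for early discontinuers. By the SAP's own rule, an Early Termination PASI taken on day 5 or later after the last dose is set aside. The ITT primary endpoint then uses a value up to 27 days old at the last dose on nominal days, up to 35 days within windows, and older if a visit was also missed. Nothing pre-specified shows the effect.

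The day counts follow from the documents. How many subjects are affected, how many change classification and in which direction cannot be derived from them. What can be said is that the number is some part of the planned 7.5-10 discontinuations per arm, at 2 points of an arm's response rate for each changed classification. At 50 per arm, two such changes would matter under the assumed rates in the table. This is a cheap improvement worth making, not a flaw in the choice of endpoint.

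**What to change.** 1. **Protocol 3.4 and 3.5.3.** Keep the request for a prompt visit. Add that the Early Termination efficacy assessment should fall within 4 days of the last dose wherever feasible, to match the SAP window. This will not always be possible when the decision to stop comes days after the last dose, so item 2 is also needed.
2. **SAP 6.4 and 6.4.7.** Keep the primary EOT definition. Pre-specify two sensitivity analyses of PASI-75 at EOT for subjects whose Early Termination PASI falls beyond 4 days:
   - (a) use that PASI if it was taken before any Protocol Table 2 therapy and before the follow-up visit, within a maximum gap that the SAP states;
   - (b) count these subjects as non-responders.
3. **Reporting.** Tabulate by arm the number of such subjects and the age of the retained value at the last dose.

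The cost is one sentence to sites, two further runs of the primary analysis on data already collected, and one table. The downside is that some values in (a) are off drug, which is why the gap needs an upper bound and (b) should stand beside it.
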